2.1 Primary Objective

This pilot study will provide feasibility on use of wearable technology for tracking and selfmonitoring PA as well as preliminary data to support our overall approach for promoting PA and improving disease status in a Hispanic women population. A larger application will be submitted to the NIH, DoD, or other federal agency focused on investigating the impact of PA on chronic neurological diseases in a diverse and inclusive Hispanic population in LA County.

2.1.1 Specific Aim 1

Specific Aim 1 establishes feasibility of this approach by measuring adherence and change in PA using a Fitbit Alta HR activity monitor in Hispanic women with chronic neurological diseases. Adherence will be determined through: (i) the average hours/day of use; and (ii) the length of time (percent of total study days) of usage throughout the 16-week study. Adherence defined as (i) 5 or more days/week of use and (ii) 10 or more hours of use during the day.

2.1.2 Specific Aim 2

Specific Aim 2 tests the hypothesis that an increase in physical activity will be correlated with a decrease in LA County (LAC) Facilities health care use (hospital and clinic visits). Physical activity will be assessed by change in either: (i) the average number of steps/week; and (ii) average time spent in sedentary, light, or moderate to vigorous intensity based on MET (metabolic expenditure) of physical activity/week. Methods: Changes in PA outcome metrics over the 16-week period will be correlated with the total number of hospital/outpatient clinic visits. Total hospital use will be determined through the LAC/DHS (Department of Human Services) electronic medical records and will include outpatient provider visits, emergency room and urgent care visits, total hospitalizations, and days spent in hospital.

2.1.3 Specific Aim 3

Specific Aim 3a tests the hypothesis that increase in physical activity is associated with an increase in the quality of life (QOL). Physical activity will be measured through: (i) the average number of steps/week; and (ii) average intensity of physical activity/week. QOL will be determined through measures of self-rated health and well-being. These Spanish validated surveys will include illness perception questionnaire and health and well-being questionnaire

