3.6.3 Determination of LA County Facilities Health Care Use

We will utilize electronic medical record (EMR) system of LA County Department of Health Services (DHS) to determine the number of hospital visits including Emergency room and urgent care visits, outpatient clinic visits, hospital stays and days within the hospital. HIPPA guidelines will be followed.

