8.0 STATISTICAL CONSIDERATIONS

8.1 Statistical Methods

Preliminary analyses will begin with an examination of the distribution of key variables to assess their characteristics (means, standard deviations, skewness, and kurtosis), to provide descriptive statistics of the study population. Continuous measures will be tested for normality and homogeneity of variance. Non-normally distributed variables will be transformed to meet the normal distribution assumption for linear statistical models.

8.1.1 Specific Aim 1

The percent of valid days of FitBit use and length of time will be calculated. We will then examine the percentage of participants who had acceptable adherence as defined as over 5 or more days/week of valid use and 10 or more hours/day length of time.

8.1.2 Specific Aim 2

Given the small sample size power to detect significant associations between physical activity and number of hospital visits will be low. Therefore, these analyses will purely exploratory. We will generate change scores from baseline to 16 weeks for both physical activity variables by subtracting week 16 scores from baseline scores. We will use Poisson regression analyses to examine the associations between changes in physical activity with our dependent variable hospital visit outcomes. Poisson regressions will be fit to account for the fact that our dependent variable (hospital visits) is a count variable and non-normally distributed. All regression models will adjust for baseline level of physical activity. Significance level will be set at 0.05.

8.1.3 Specific Aim 3

All analyses described for aim 3 are also exploratory in nature as the proposed analyses will be underpowered to detect a significant association. Change scores in Quality of life, symptoms of anxiety and depression will be calculated by subtracting week 16 scores from baseline scores. Linear regression analyses will be run examining the associations between change in PA and our dependent variable of change.

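### The Aim 2 health-care-use outcome lists admissions and their hospital days under one visit count, with no counting rule and no overdispersion handling for the Poisson model

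*Combined protocol and SAP*

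**What the plan says.** Three sections describe the Aim 2 dependent variable.

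- **Section 2.1.2** says changes in activity "will be correlated with the total number of hospital/outpatient clinic visits". The next sentence says total hospital use "will include outpatient provider visits, emergency room and urgent care visits, total hospitalizations, and days spent in hospital".
- **Section 3.6.3** uses the county electronic record "to determine the number of hospital visits including Emergency room and urgent care visits, outpatient clinic visits, hospital stays and days within the hospital". Stays and days therefore sit under a single number of visits.
- **Section 8.1.2** refers to "our dependent variable hospital visit outcomes", in the plural, and then justifies the model on the ground that "our dependent variable (hospital visits) is a count variable and non-normally distributed", in the singular. The models adjust for baseline activity and use a 0.05 level. The section calls the analysis exploratory because power is low.

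No section says whether the components are added or analysed one at a time. None says how an admission, its days and a linked emergency visit are to be counted. None mentions a dispersion parameter, a robust variance or an alternative to the plain Poisson model.

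**The concern.** A Poisson model takes the variance of the count to be equal to its mean, as it would be for independent events. Days of one hospital stay are not independent events: once a woman is admitted, they arrive together. If they enter the outcome, the variance exceeds the mean, the model's standard errors are too small and its p-values too low. If the components are also summed, the same admission is entered as a stay, again as its days, and possibly again as the emergency visit that led to it.

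With 20 women, a single long stay could then produce an apparent link between activity and health-care use. Section 2.1.2 states a directional hypothesis, 3.6.3 stands among the primary outcome measures, and 2.1 says the pilot's preliminary data are meant to support a larger funding application. The low power noted in 8.1.2 is a warning about missed associations. The risk here is the opposite one, a spurious association.

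**Working it through.** **Inputs from the documents.** n = 20 in a single group (3.2); 16 weeks of record review (3.1); Poisson regression on activity change, adjusted for baseline activity, at level 0.05 (8.1.2). Sidedness is not stated, so two-sided is assumed. The plan gives no visit rate, admission rate, length of stay or power figure, so there is no planned figure to reproduce.

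**Assumed inputs.** Mean of 2-4 routine visits per woman over 16 weeks; 5-20% of women admitted; mean stay 3-10 days; each admission entered through the emergency room; no true association.

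**Step 1: units added by one admission if the components are summed.** Units = 1 (emergency visit) + 1 (stay) + L (days).

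- L = 3: 5 units. L = 5: 7 units. L = 10: 12 units.
- Share of the cohort total = units / (20 × visits per woman + units). With 3 visits each: 5/65 = 7.7%, 7/67 = 10.4%, 12/72 = 16.7%.
- With 2 to 4 visits each, a 5-day stay makes up 14.9% down to 8.0% of all units, and a 10-day stay 23.1% down to 13.0%.

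**Step 2: worked example.** Twenty women have 3 visits each, and the woman with the lowest activity change also has one admission. Poisson regression on standardised activity change alone (baseline activity left out for simplicity) gives:

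| Outcome | Rate ratio per SD | p |
|---|---|---|
| Sum, 3-day stay | 0.85 | 0.22 |
| Sum, 5-day stay | 0.80 | 0.09 |
| Sum, 10-day stay | 0.70 | 0.005 |
| Admission counted once | 0.97 | 0.80 |

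**Step 3: false-positive rate of the summed count.** Simulation with n = 20, activity change and baseline activity in the model, and 3,000 runs per scenario; 5-10% admitted and means of 2 and 4 routine visits:

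| Mean stay | Rejection at nominal 5% |
|---|---|
| 3 days | 6.5-12.8% |
| 5 days | 9.9-18.2% |
| 10 days | 18.3-32.8% |

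Pearson dispersion ran from 1.2 to 3.9. Taking the share admitted up to 20% raises the top of the range to about 40%.

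**Step 4: separate models.** If each component has its own Poisson model, days in hospital become an outcome in their own right. Among simulated cohorts with at least one admission, the days-only model rejected in 18-52% of trials.

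**Step 5: does counting once suffice?** If the remaining visits are truly Poisson, counting each admission once brings rejection to 4.4-5.3%. That result depends on all women sharing one visit rate. When rates vary between women (gamma shape 4, 2, 1; mean 3.5 visits; 10% admitted), the once-per-encounter count rejects in 14%, 24% and 32% of trials, against 4% without such variation. A separate run gave 14-26%, and about 3-6% once the variance was scaled by the estimated dispersion.

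**Step 6: does scaling alone suffice?** A dispersion-scaled variance applied to the summed outcome gives 4.8-7.6% in the Step 3 scenarios. It removes most of the inflation but not all, and it leaves the multiple counting in the estimate.

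**The case against.** The strongest reply is that the plan never says the components are added. A reader might infer a sum from the words total and number, but the list in 2.1.2 can also be read as what will be extracted from the record, and the plural in 8.1.2 allows one model per measure. This stands: summation is a permitted reading, not a stated one. It does not rescue the plan, because separate models would make days a Poisson outcome (Step 4). A third reading, that days are extracted but never modelled, would avoid the problem. However, no section says so, and 3.6.3 puts days inside the visit count.

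Second, every rate is assumed. The upper end needs long stays among women who walk unaided and have no condition that precludes exercise. At 5% admitted, the chance of no admission in the cohort is 0.95^20 = 36%, and there is then no distortion from this source. This also stands, and it is why a range is given.

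Third, variation in visit rates between women could inflate error as much as the counting does. In the Step 5 setting with a 5-day mean stay, the sum rejects in 22%, 27% and 35% of trials, not far above the once-only count. This stands, and it makes the dispersion scaling necessary.

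Fourth, the aim is exploratory, feasibility is the primary goal, and no decision rule rests on this p-value. That limits the consequence, although a 0.05 threshold is still set.

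**Conclusion.** The concern holds in a limited form. The Aim 2 count is not defined, its wording places stays and their days under one number of visits, and the Poisson model has no protection against the resulting overdispersion. Under the assumed rates (5-20% admitted, mean stay 3-10 days, n = 20), the false-positive rate of a summed count is about 7-40% at a nominal 5%. It is near the lower end with short stays and low admission rates.

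Three stronger conclusions are tempting, and the documents do not support them:

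- **That the plan adds the components and one admission dominates the result.** No sentence states a sum, and in the scenarios of Step 1 a single 5- or 10-day episode makes up 8-23% of all units.
- **That counting each admission once restores the nominal error rate.** It does so only if women share one visit rate, which is unlikely with mixed neurological conditions.
- **That acute and routine use must be analysed apart.** The hypothesis in 2.1.2 covers hospital and clinic use together, and nothing in the documents shows the two moving in opposite directions.

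**What to change.** Before analysis, amend 2.1.2, 3.6.3 and 8.1.2 consistently:

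1. Define the Aim 2 outcome as the number of separate encounters over the 16 weeks, each counted once. An emergency visit that leads to admission counts once, as the admission.
2. Report days in hospital descriptively and keep them out of any Poisson outcome.
3. Fit the model with a dispersion-scaled (quasi-Poisson) variance and report the estimated dispersion.

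Reporting acute and outpatient encounters side by side is an optional descriptive addition. Making them two tested outcomes would add tests in 20 women and leave a sparse acute count.

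The cost is protocol wording, a simple coding rule for the electronic record and a slightly wider interval. No new data are needed, since 3.6.3 already collects every component.

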3.0 STUDY DESIGN

3.1 Overall Study Design

This is a 16-week single group study of PA promotion and monitoring along with its effect

on Neurological Health. Twenty Hispanic women seen at LAC/USC Neurology clinic will be referred to TWC and invited to participate in a physical activity (PA) study for 16 weeks. Participants will receive individualized Fitbit Charge activity monitors at baseline and instructed on its usage and maintenance. Adherence to activity monitor use and amount and level of PA will be determined. All assessments that include quality of life, exercise behaviors, and self-rated health and mood will be made at baseline and at 16 weeks at TWC. Educational/coaching will take place through (i) individualized instruction on exercise at baseline and at the end of week 4 at TWC and (ii) weekly calls from TWC to promote PA goal setting as well as Fitbit use. At the end of week 1, participants will be asked to return to the TWC to review instructions on Fitbit App use and to receive further education on the benefits of exercise through a brief Power Point presentation. Patient may also receive text messages throughout the study to remind them of upcoming appointments or deadlines. General Neurological Health status will be determined through use of Electronic medical records to determine hospital and outpatient clinic visits through the 16 weeks. At study completion, participants will be allowed to keep their Fitbit activity monitor and will receive a 3-month follow up post-study call to assess the continued usage of the Fitbit charge activity monitor and a quality of life questionnaire.

3.2 Enrollment Plan

Twenty (20) Hispanic women with a chronic neurological disorder will be recruited from our LAC/USC Neurology Clinic. We expect to achieve this goal by 2 months from study start.

3.3 Participant Identification and Informed Consent

For this study, Drs. [name] or [name] will screen all potential participants according to the list of inclusion/exclusion criteria. This will include talking to the referral neurology doctor from the neurology clinic to determine there are no limitations to physical activity/exercise (see exclusion below) .The principal investigators and members of the research team will explain the purpose, risks, procedures, and date of the study. If the subject is interested in participating, she will be given the Informed Consent to read or if they cannot read, our coordinator will read the informed consent to her. Subjects and their family members will be allowed sufficient time to read and/or think about the Informed Consent Form and be given the opportunity, and encouraged, to ask questions before signing the document. Following the patient giving informed consent (signing the document) she will be able to participate in the study. If the investigator or study team members have any reason to suspect that the subject does not fully comprehend the informed consent or the study, the individual will not be considered as a possible participant of the study. The study will be conducted after having Institutional Review Board (IRB) approval at USC.

3.4 Fitbit Charge HR2 Activity Monitor

Participants will be provided a Fitbit Alta HR and wall charger. Each participant will be given a unique ID# that will be assigned at baseline and used to set-up the Fitbit data acquisition. The Fitbit app will also be set up on their smartphone to allow self-monitoring of activity. The Fitbit device includes both an accelerometer and heart rate monitor and is capable of continuous measuring and storing data at up to a 1-second sampling rate for up to 5 days. Fitbit data will be passively downloaded through either a WiFi and/or smartphone connection to Fitabase. Fitabase (Fitabase, San Diego, Ca) is a research friendly application programming interface and comprehensive data management program that allows the device data from all users to be identified through a uniquely assigned ID# and transmitted in a secure fashion to the data acquisition and integration center.

The Fitbit Alta will be worn on the wrist every day during the course of the 16-week study. While the Fitbit is water resistant, participants will be asked not to wear the device while bathing or swimming. Participants will be instructed on self- monitoring, usage and maintenance of the Fitbit at the baseline visit. Participants will be monitored for Fitbit compliance by (i) weekly phone calls; and (ii) monitoring of passively downloaded Fitbit data through Fitabase data collection server. Further instructions will also be given 1 week into the study, to ensure proper compliance. Participants will be allowed to keep their Fitbit monitor at the end of the study. Follow-up phone call at 3-months post-study will assess continued use of the Fitbit activity monitor.

3.5 Educational/Behavioral Coaching on Exercise (Lifestyle Redesign)

Participants will receive individualized goal setting and a guide to increase exercise at the beginning of the study (baseline) and at week four (week four visit) at TWC. The Occupational therapist (OT) will administer a well published approach for promoting PA called Lifestyle Redesign which addresses physical, psychosocial and environmental barriers to health and incorporate self-care strategies and goal setting. Coaching will be administered by a bilingual OT ([name]) and in language (Spanish or English) preferred by participant. Based on studies examining PA and brain health, the Occupational Therapist (OT) will guide the participant through a goal setting process for moderate to vigorous intensity of physical activity including a specific guide plan to achieve these goals of 10,000 steps per day and/or 150 minutes/week of moderate to vigorous activity. Participants will also receive weekly calls from the TWC (supervised by OT) to review PA and goal setting for each week over the course of the 16-week study.

3.5.1 Motivation to Exercise

Participants will be given a brief Power Point presentation titled "Promoviendo un Cerebro Sano En las Enfermedades Neurologicas, el Rol Del Ejercicio". The purpose of this presentation is the educate participants on the importance of exercise for brain health and increase motivation throughout the study. This presentation will be given at baseline visit, week 1, and week 4 follow up.

3.6 Primary Outcome Measures

3.6.1 Baseline Demographic Data

Following inclusion and exclusion and after obtaining informed consent, baseline demographic data will be obtained which will include age, recent healthcare visit frequency, medical history, medication, years of education, and tobacco use.

3.6.2 Physical Activity, Adherence Assessment

Data gathered from Fitbit based device will be stored, visualized and aggregated through a commercially available service (Fitabase Inc, Https://www.Fitabase.com). Fitabase is a research friendly application

programming interface that allows the device data from all users to be identified through a uniquely assigned ID# and transmitted in a secure fashion to the data acquisition and integration center. Data is downloaded from Fitabase in a de-identified matter and is ready for statistical analysis (i.e. CSV files that are SPSS ready). The Fitabase one-time set-up process (taking approximately five minutes) will take place at the wellness center to establish a continuous, passive and secure data stream of all measures. The following measures will be obtained during the course of the study: (i) step count, (ii) time spent in sedentary, light, moderate, and vigorous activity, and (iii) length of wear.

3.6.3 Determination of LA County Facilities Health Care Use

We will utilize electronic medical record (EMR) system of LA County Department of Health Services (DHS) to determine the number of hospital visits including Emergency room and urgent care visits, outpatient clinic visits, hospital stays and days within the hospital. HIPPA guidelines will be followed.

3.7 Secondary Outcome Measures (scales in Spanish and English)

All scales will be offered to patient in their preferred language of Spanish or English. For patients who are illiterate, the coordinator will read the scales to the patient and record their answer.

3.7.1 **Quality of Life (QOL)**

This measure assessed participants' views of their health, how well they feel, and well they are able to complete their usual activities.

3.7.2 Spanish Acculturation

The purpose of this questionnaire is to assess the level to which participants acculturate or adopt the attitudes, values, customs, beliefs, and behaviors of another culture.

3.7.3 Brief Illness Perception Questionnaire (BIPQ)

The purpose of this questionnaire is to assess participants' perceptions of their health and well-being.

3.7.4 Patient Activation Measure (PAM)

This measure assesses participants' knowledge, skill, and confidence for managing one's health and healthcare.

3.7.5 Spanish Physical Activity Questionnaire

This self-administered questionnaire determines total physical activity (METh week⁻¹) and total number of hours sitting down across a week to evaluate the levels of participants' physical activity and sedentary lifestyle.

3.7.6 FitBit Wear Technology Questionnaire

The purpose of this questionnaire is to ascertain the participants' opinions on how intuitive and useful the FitBit phone application and FitBit Alta HR activity monitor are and whether they think the device might be helpful in encouraging them to exercise or improve their physical fitness.

4.0 SELECTION AND WITHDRAWAL OF SUBJECTS

4.1 Inclusion Criteria

Inclusion Criteria includes (1) Women of Hispanic origin; (2) established patient of the neurology clinic defined as clinic visits at the LAC/USC Neurology Clinic that have spanned greater than one year; (3) age \geq 30 (4) willing and able to utilize a Fitbit activity Monitor; (5) own a smart phone device; (6) ambulatory without assistance; (7) willing and able to provide informed consent; (8) within commuting distance to the wellness center and LAC/USC hospital; (9) reads or comprehends Spanish; (10) weekly internet access.

4.2 Exclusion Criteria

Exclusion Criteria includes (1) Clinically significant neurological or psychiatric illness including mental retardation, dementia or severe depression/anxiety; (2) any physical condition that precludes engagement in exercise, including significant heart disease.

4.3 Withdrawal Criteria

Participants may withdraw from the study at any time for any reason without affecting his/her care.

